#### **3.3. Design**

The purpose of this study is to evaluate the safety and effectiveness of the Spatz3 in subjects with a BMI  $\geq 30$  and  $< 40$  who have failed to achieve and maintain weight-loss with a weight control program.

Subjects will be studied in a randomized, controlled, multi-center study. The control group will receive dietary/exercise counseling for 32 weeks. The treatment group will receive dietary/exercise counseling plus the Spatz3 balloon for 32 weeks.

The study will run 32 weeks for the control group and 32 weeks followed by a 24-week follow up period for the treatment group.

282 eligible subjects will be randomized to treatment (188 subjects) or control (94 subjects) arms. All treatment group subjects will undergo endoscopy and those without endoscopic contraindications will be implanted with the Spatz3 balloon for 32 weeks. All subjects will follow a 1000-1200 kcal/day-deficit diet during their participation in the study.

At 18 weeks  $\pm$  4 weeks, treatment arm subjects will be evaluated, and those that meet the criteria described below in section 4.3.3.2.4 will undergo an adjustment procedure wherein the balloon volume will be increased to achieve extra weight loss. The balloon adjustment procedure is done with an endoscopy procedure under the same sedation as the implantation procedure. At the end of the 32-week treatment period the control subjects will be dismissed and the treatment group will be explanted and will have a 24-week follow up.

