#### 7.1.2. Primary Endpoints

The co-primary hypotheses are as follows:

1. The mean %TBL in the Spatz3 group exceeds that in the control group by 4.5%. In formal terms, this is:

$$H_0: \mu_S - \mu_C \leq 4.5\%$$

vs.

$$H_A: \mu_S - \mu_C > 4.5\%,$$

where  $\mu_S$  and  $\mu_C$  are the population mean %TBL for the Spatz3 and control groups, respectively.

2. The response rate in the Spatz3 group is superior to a performance goal of 50%, where a responder is defined as a  $\geq 5\%$  loss in total body weight at 32 weeks. In formal terms, this is:

$$H_0: \pi \leq 50\%$$

vs.

$$H_A: \pi > 50\%,$$

where  $\pi$  is the population response rate in the Spatz3 group.

All missing body weight data will first be imputed as follows. Initially, all interim missing data (missing data for which there is at least one subsequent non-missing body weight) will be linearly interpolated based on the last and subsequent non-missing body weight. If a subject in the Spatz3 group has the balloon explanted, the body weight immediately preceding the explant will be used and the subject will be treated as a dropout from that time forward, even though the subject will be followed for another 24 weeks. After the interim missing data have been interpolated, all additional missing data will be imputed using a regression method for multiple imputation. Baseline body weight, baseline BMI, subject's gender, study center, treatment group, and all non-missing body weight measurements through Week 32 will be included in the imputation model. A total of five imputed datasets will be created. The first primary endpoint, %TBL at 32 weeks, will be analyzed by an analysis of covariance that includes the effects of treatment group, study center, baseline BMI group ( $< 35 \text{ kg/m}^2$  vs.  $\geq 35 \text{ kg/m}^2$ ) and subject's gender as covariates. The parameter estimates from the five imputations

will be used to estimate a one-sided lower 97.5% confidence bound on the difference in mean %TBL (Spatz3 mean minus control mean). If this lower confidence bound exceeds the super-superiority margin of 4.5% the Spatz3 will be deemed to have super-superiority over the control group in %TBL.

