The second primary endpoint will be analyzed using the same five imputed datasets created for testing the first primary endpoint, but only the data from subjects in the active treatment group. The estimated proportion of subjects with a  $\geq 5\%$  weight loss at Week 32, along with their associated variance, from each dataset will then be combined using Rubin's method to estimate the overall proportion and its variance. This proportion and its variance will then be used to estimate the one-sided lower 97.5% confidence bound on the proportion of subjects with a  $\geq 5\%$  weight loss at Week 32. If this lower confidence bound exceeds 0.50 the second primary hypothesis will be rejected, and the Spatz3 will be deemed to have met its second primary hypothesis.

As a sensitivity analysis of each co-primary endpoint, an LOCF imputation procedure will be employed in which all missing data among subjects with at least one post-randomization body weight measurement are replaced by the last non-missing value.

Secondary analyses of the primary endpoints will be per protocol and will include subjects according to the actual treatment received and will exclude subjects who did not meet the inclusion criterion of baseline BMI  $\geq 30 \text{ kg/m}^2$  and  $< 40 \text{ kg/m}^2$ .

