### **7.1.4. Subgroup Analyses**

The following subgroup analyses will be performed:

- Study site
- Gender
- Baseline BMI ( $< 35 \text{ kg/m}^2$  vs.  $\geq 35 \text{ kg/m}^2$ )
- Age ( $< 45$  years vs.  $\geq 45$  years)
- Race (white vs. all others)

Subgroup analyses of the first primary endpoint will be performed on the average of the five imputed datasets. For each subgroup, the subgroup and its interaction with treatment group will be added to the primary analysis model. A significant interaction with treatment group ( $p < 0.05$ ) will indicate that the mean %TBL differences between the Spatz3 and the control were not comparable between (among) the levels of the subgroup. If a significant interaction is found for any subgroup, additional analyses will be performed in an attempt to determine the cause of the interaction.

It should be noted that a formal subgroup analysis to compare subjects who did and did not receive a change in balloon volume must be assessed with caution. This is because the decision to have the change is optional and a meaningful comparison of its effect could only be done if subjects were randomized to volume addition or not. However, to characterize the risk profile of the Spatz3 and on its effect on weight loss, sub-group analyses by number of adjustments and on balloon volumes will be performed based on the following balloon volume sub-groups:

- 400-600 cc - includes mostly study subjects with initial filling volume only
- 601-800 cc – includes subjects who have had one additional adjustment
- 801-1000cc – includes subjects who have had at least 2 upward adjustments

These analyses will evaluate their effects on the first primary endpoint and on adverse events.

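### Section 7.1.2 specifies neither imputation by arm nor treatment-by-weight terms, so the %TBL comparison with the 4.5-point margin may rest on slopes that are wrongly shared by both arms

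*Combined protocol and SAP*

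**What the plan says.** Section 7.1.2 first interpolates interim gaps linearly. After that, "all additional missing data will be imputed using a regression method for multiple imputation". The listed inputs are baseline weight, baseline BMI, gender, "study center, treatment group, and all non-missing body weight measurements through Week 32 will be included in the imputation model". No equation is given, no interaction is named or excluded, and imputation by arm is not mentioned. Section 7.1.5 only refers back to 7.1.2.

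Three further provisions matter here:
- For a Spatz3 subject explanted early, "the body weight immediately preceding the explant will be used and the subject will be treated as a dropout from that time forward". Read plainly, that subject's Week 32 value is imputed although follow-up continues.
- For the responder endpoint, the section describes an analysis "using the same five imputed datasets created for testing the first primary endpoint, but only the data from subjects in the active treatment group".
- LOCF is the only missing-data sensitivity analysis: "As a sensitivity analysis of each co-primary endpoint, an LOCF imputation procedure will be employed".

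**The concern.** A programmer working from the list would most naturally fit one regression to both arms, with a treatment term beside the earlier weights. The treatment term lets the arms' means differ. It does not let the relation between an earlier weight and the Week 32 weight differ.

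There is reason to doubt a common relation. Only Spatz3 subjects can have their treatment changed between the early visits and Week 32. Section 3.3 describes a procedure at about 18 weeks "wherein the balloon volume will be increased to achieve extra weight loss", and section 4.3.3.2.5 adds an early volume addition for lack of effect and volume reductions for intolerance or ulcer. Controls receive counseling throughout.

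The first co-primary claim depends on a single lower confidence bound exceeding 4.5 points, so a bias of a few tenths of a point bears directly on its error rate or its power.

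**Working it through.** **The plan's own figure (section 7.2).** Inputs: means 10.34% and 3.3%, SD 6.6%, margin 4.5, one-sided 2.5%, power 80%, allocation 2:1, dropout 15%.
- Distance beyond the margin: 10.34 − 3.3 − 4.5 = 2.54.
- Control n = (1.960 + 0.842)² × 6.6² × (1 + 1/2) / 2.54² ≈ 79.5, so 80; total 240, power 80.2%.
- 240 / 0.85 = 282.4, against 282 stated.
- SE at 160/80 = 6.6 × √(1/80 + 1/160) = 0.904.

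The stated size is reproduced. The documents give no figure for the imputation model.

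**Bias from shared slopes.** In large samples the bias in one arm's mean is about

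dropout share × (pooled slope − arm slope) × (dropout minus completer mean early loss).

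With equal dropout share and an equal early-loss gap in both arms, the pooled slope cancels:

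bias in difference ≈ dropout share × (Spatz3 slope − control slope) × gap,

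where gap is completer minus dropout mean early loss.

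**Check by large-sample simulation.** It used 600,000 subjects per run, four runs per scenario, 15% dropout, and the Week 32 means and SD of section 7.2. Early-loss means of 7 and 2.5, early SD of 4, the slopes and the dropout mechanism are assumptions.

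| Slopes Spatz3/control | Gap | Formula | Simulated bias in difference | Shift in response rate (percentage points) |
|---|---|---|---|---|
| equal | about 3.5 | 0 | −0.002 | 0.00 |
| 1.2/0.8 | about 0 | 0 | 0.000 | +0.01 |
| 1.2/0.8 | 2.64 | 0.15 × 0.4 × 2.64 = 0.16 | +0.16 | +0.3 |
| 1.2/0.8 | 4.67 | 0.15 × 0.4 × 4.67 = 0.28 | +0.28 | +0.6 |
| 1.4/0.6 | 4.68 | 0.15 × 0.8 × 4.68 = 0.56 | +0.56 | +1.2 |
| 0.8/1.2 | 4.65 | 0.15 × (−0.4) × 4.65 = −0.28 | −0.28 | −0.5 |
| 0.6/1.4 | 4.65 | 0.15 × (−0.8) × 4.65 = −0.56 | −0.56 | −1.1 |

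At heavier assumed dropout (30% in both arms, or 20% and 35%) with slopes of 1.4 and 0.6, either way round, the bias reached about 1.05 to 1.07 points in size. With an arm-by-early-weight interaction and arm-specific residual spread, which is equivalent to imputing by arm, the bias was at most 0.006 points and 0.04 percentage points in every scenario.

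**At the trial's size (188/94, five imputations, about 14% missing at random).**
- One early weight, 1,500 trials per scenario, slopes 1.2/1.0, 1.4/0.9 and 1.6/0.8: bias +0.08, +0.19 and +0.33. By-arm imputation gave −0.01 to +0.01. Reversing the slopes gave −0.23.
- Ten centers, ten visits, visit-by-visit regression and the planned ANCOVA at a true difference of 4.5, 800 trials per scenario: bias +0.03, +0.19 and +0.28, with rejection of 2.6%, 3.7% and 4.3% (Monte Carlo error about 0.6–0.7 points).
- A further run with ten centers at a true difference of 4.5: bias +0.17 to +0.32, with rejection of 3.5% to 5.8%. Reversed slopes gave −0.20. By-arm and interaction models gave about zero.

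**What such a bias does, using SE 0.904.**
- Error at the margin, 1 − Φ(1.96 − bias/0.904): +0.2 gives 4.1%; +0.3 gives 5.2%.
- Power, Φ((2.54 + bias)/0.904 − 1.96): −0.2 gives 73.5%; −0.3 gives 69.8%; −0.5 gives 61.7%.

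**Responder endpoint.** Under normality the plan's mean and SD imply Φ((10.34 − 5)/6.6) = 79% responders, about 29 points above the goal of 50%. The largest shift in any scenario was 1.8 points.

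**The case against.** The strongest reply is that the text is silent, not wrong. A reader might infer that 7.1.2 enters treatment as a main effect only and so forces common slopes. The section does not say that, and by-arm imputation or interaction terms would also fit its wording. This stands: the defect is under-specification, with pooled main effects as the plainest reading.

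A reader might also infer that different weight trajectories are enough to cause bias. They are not. Equal slopes with different means gave −0.002, and unequal slopes with completely random dropout gave 0.000. Both conditions are needed. The balloon and the later volume addition show that means may differ; they make unequal slopes plausible but do not establish them.

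Nor do the documents support a claim that the device effect is inflated. They do not say who drops out. Section 4.3.3.2.5 adds volume early for subjects without balloon effect and withholds the 18-week addition from symptom-free subjects at goal weight. Either could flatten the Spatz3 slope and reverse the sign.

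Finally, by-arm imputation is not free. With up to ten centers, 94 controls average 9.4 per center against about 20 predictors. In one run its mean SE rose from 0.89 to 0.92 and rejection at the margin fell to about 1.9%. That argues for interactions, or for pooling small centers, but not for leaving the model unstated.

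**Conclusion.** The point holds as an under-specified imputation model for the first co-primary endpoint. On its plainest reading, 7.1.2 can bias the %TBL difference by roughly 0.2 to 0.3 points in either direction, with one-sided error of about 3.5% to 6% or power falling to about 70–74%. This rests on assumed slope differences of 0.4 to 0.8, about 14–15% dropout, and dropouts who differ from completers in early weight. Smaller slope differences leave the error rate indistinguishable from nominal. Strong dependence of dropout on early loss, or heavier dropout, makes the bias larger.

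The bias arises with data missing at random, the premise on which the planned imputation rests. LOCF would not show it: LOCF holds weight at its last value, so neither agreement nor disagreement with the primary result speaks to the slopes.

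Two wider readings go too far. Because the same datasets feed the responder endpoint, a reader might infer that both co-primaries are at risk, but a shift of at most 1.8 points is negligible against about 29 points of assumed headroom. A reader might also expect the treatment interactions in section 7.1.4 to be pulled toward null. That is possible in principle, but no size has been established, and those tests are neither primary nor secondary endpoints.

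**What to change.** In section 7.1.2, state that the regression imputation will include interactions of treatment group with the earlier body weights. Alternatively, state that it will be run separately within each randomized arm, with small centers pooled by a pre-stated rule for the imputation step only. Leave the ANCOVA, the five imputations and Rubin pooling as they are.

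The cost is one sentence and a small program change, with no new data and no change to the 282 subjects. The standard error rises slightly: under 1% with interactions, and about 1–4% with imputation by arm.

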#### **7.2. Sample size**

The true population mean %TBL in the control group is assumed to be 3.3% based on the Orbera and ReShape PMA studies. The standard deviation of %TBL is assumed to be approximately 6.6%, based on 6-month data from the Orbera PMA study. Based on these two assumptions, and a true population mean %TBL in the Spatz3 group of 10.34%, a total sample size of 240 subjects randomized 2:1 (160 in the Spatz3 group and 80 in the control group) will provide 80% power to demonstrate super-superiority of 4.5% TBL over the control at a one-sided significance of 2.5%. To account for a potential dropout rate of 15%, the final total sample size is 282 subjects randomized 2:1 (188 in the Spatz3 group and 94 in the control group).

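### Five imputations with no prespecified seed leave a borderline result on the %TBL co-primary partly to Monte Carlo noise; more imputations and a fixed seed would largely cure this

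*Combined protocol and SAP*

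**What the plan says.** Section 7.1.2 handles missing weights in two steps. Gaps with a later weight are interpolated; after that, "all additional missing data will be imputed using a regression method for multiple imputation". Device subjects whose balloon is removed early count as dropouts from that point, so their later weights are imputed too. The number of imputations is fixed: "A total of five imputed datasets will be created".

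The decision rule for the first co-primary is a single comparison: "If this lower confidence bound exceeds the super-superiority margin of 4.5% the Spatz3 will be deemed to have super-superiority". For the responder co-primary: "The second primary endpoint will be analyzed using the same five imputed datasets created for testing the first primary endpoint". Sections 7.1.3 (excess-weight responder endpoint) and 7.1.4 (subgroups) reuse the same five datasets.

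The plan gives no seed, no tolerance for Monte Carlo error and no repeat with more imputations. The only alternative imputation is LOCF, which says nothing about dependence on the seed. Section 7.2 allows for 15% dropout.

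**The concern.** Regression imputation draws random values. With five draws, both the pooled estimate and the between-imputation variance carry visible simulation error, so the lower bound shifts when the seed changes. The bound is then held against a fixed 4.5-point margin. Near that margin, two analysts who follow the plan faithfully on identical data, but with different seeds, could report opposite results on a pivotal endpoint. Because no seed is prespecified, the plan also has nothing that would rule out rerunning a borderline analysis.

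**Working it through.** **Inputs from section 7.2.** Control mean 3.3, device mean 10.34, SD 6.6, margin 4.5, one-sided 2.5%, 160/80 evaluable, 15% dropout, 188/94 randomized.

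**The plan's own sample size.** Excess over the margin = 10.34 − 3.3 − 4.5 = 2.54. SE = 6.6 × √(1/160 + 1/80) = 0.904. Power = Φ(2.54/0.904 − 1.96) = 80.2%, as stated. 240/0.85 = 282.4, stated as 282. The figures reproduce.

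**How near the margin the bound is likely to fall.** Expected clearance = 2.54 − 1.96 × 0.904 = 0.77 points. From trial to trial the bound varies with an SD of about 0.90. The chance that it lands within 0.2 points of the margin is Φ(−0.633) − Φ(−1.078) = 0.263 − 0.141, about 12%. Within 0.4 points it is Φ(−0.411) − Φ(−1.300) = 0.341 − 0.097, about 24%.

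**Analytic size of the noise.** The seed-to-seed SD of the pooled estimate is √(B/m), where B is the between-imputation variance; this is about √(FMI × SE²/m), with FMI the fraction of missing information. With FMI 0.15 and SE 0.905, m = 5 gives √(0.15 × 0.819/5) = 0.157 points, and m = 100 gives 0.035.

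**Simulation of the bound.** 188/94 subjects, true difference 7.04, SD 6.6, Bayesian regression imputation, Rubin's rules with small-sample degrees of freedom; 250 trials and 40 seeds per scenario. Not in the documents and therefore assumed: missing fractions other than 15%, the correlation of an earlier weight with week-32 %TBL, dropout completely at random, and no center, BMI or gender covariates.

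| Missing, device/control | Correlation | Seed SD of bound, m=5 | Two seeds disagree, m=5 | Disagree, m=50 | Seed SD, m=100 | Disagree, m=100 |
|---|---|---|---|---|---|---|
| 8%/8% | 0.8 | 0.070 | 2.4% | 0.8% | 0.015 | 0.5% |
| 15%/15% | 0 | 0.207 | 6.6% | 2.4% | 0.040 | 2.1% |
| 15%/15% | 0.6 | 0.151 | 4.2% | 1.5% | 0.031 | 1.0% |
| 15%/15% | 0.8 | 0.104 | 3.4% | 0.7% | 0.022 | 0.6% |
| 25%/15% | 0.6 | 0.183 | 6.8% | 1.7% | 0.037 | 1.2% |
| 25%/25% | 0 | 0.333 | 11.7% | 2.5% | 0.061 | 1.8% |
| 25%/25% | 0.6 | 0.240 | 9.8% | 2.7% | 0.045 | 1.9% |

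With 250 trials per row, the decimals are not firm. A separate simulation with eight visits and dropout spread over them gave, at m = 5, 0.14 points and 5.1% at 15% missing, 0.16 and 5.7% at 22%/15%, and 0.23 and 9.4% at 30%/25%.

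At 15% missing, 9% to 18% of simulated trials had a pass probability over seeds between 5% and 95% with m = 5, against 2% to 6% with m = 100. Power with m = 5 against m = 100 was 76.2% against 77.7%, 81.3% against 81.9%, and 84.1% against 84.7%: a loss of 0.6 to 1.5 points.

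**Responder co-primary.** Under normality the planning values imply Φ((10.34 − 5)/6.6) = Φ(0.809), about 79% responders against the 50% goal. The seed SD of its lower bound was 0.004 to 0.012, and it passed in every run.

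**The case against.** The strongest reply is that five imputations are statistically sound. Rubin's variance includes the factor (1 + 1/m), and the degrees of freedom allow for small m. Section 7.1.2 names Rubin's method for the responder endpoint; I assume the same pooling for %TBL. On that basis a reader who infers an invalid or biased test, or an inflated type I error, goes further than the plan supports. This part of the reply stands.

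Second, disagreement between two runs needs two seeds. A fixed seed and software would make even five imputations repeatable. That is true, but the answer would be repeatable and still arbitrary near the margin; only a larger m makes it stable.

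Third, one might infer from the 0.77-point clearance that a result on target could flip. It would not: 0.77 is 3.7 seed SDs at 0.21 and 7.7 at 0.10. Only bounds close to 4.5 are exposed.

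Fourth, the heavier scenarios lack a source. The documents give 15% dropout, and section 2.2 reports 4.2% to 6.7% early removals in reviews of an earlier balloon. If removals came on top of the 15%, device-arm missingness would be at most about 15 + 6.7 = 21.7%. The documents do not say whether the 15% already includes them, so 25% to 30% is an assumption only.

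It is also tempting to suppose that the missing seed reflects an intention to rerun. Nothing in the documents suggests that; the gap is only that rerunning is not ruled out.

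**Conclusion.** The point holds as a modest, cheaply avoided weakness in reproducibility for the %TBL co-primary. At the planned 15% missing, five imputations give a seed-to-seed SD of the bound of about 0.10 to 0.21 points and opposite verdicts from two seeds in about 3% to 7% of trials. With 25% to 30% missing in the device arm, disagreement is about 7% to 12%. With 100 imputations it is about 0.5% to 2% in every scenario tried, so the dependence is greatly reduced but not eliminated.

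A clear win or loss does not change with the seed. The responder co-primary shares the datasets but is practically unaffected at planning values. The sizes rest on the planning mean and SD and on the assumed correlations and random dropout. The direction does not depend on them.

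**What to change.** In section 7.1.2, replace five with a larger number of imputed datasets, for example 100; 50 performs nearly as well (0.7% to 2.4% disagreement at 15% missing). Prespecify the random seed and the software with its version. Carry the same datasets through the responder co-primary, the excess-weight responder endpoint in section 7.1.3 and the subgroup analyses in section 7.1.4.

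No endpoint, margin, sample size or data collection changes. Since the number stands in the protocol itself, the cost is a minor amendment, submitted to FDA and the IRBs as appropriate under section 10.2, and a little more computing. Section 13 shows that the statistical analysis was already revised in this way in versions 1.4 and 1.4a.

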#### **3.2. Endpoints**

##### **3.2.1. Effectiveness**

There are two co-primary effectiveness endpoints:

- Percent change in total body weight (%TBL) at 32 weeks; and
- Clinical response, where a responder is defined as a subject with at least a 5% loss in total body weight at 32 weeks

There are two secondary endpoints:

- Maintenance of 40% of the total body weight loss with the balloon six months after the balloon is removed
- Clinical response, where a responder is defined as a subject with at least a 25% loss in excess body weight at 32 weeks

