**Figure 1: Study Timeline**

#### 4.3.1. Screening and Eligibility Assessment

Screening will be conducted by the investigator or co-investigator and documented on the PI Intake form (*Appendix E2: CRF\_2 PI Intake*) and Screening Labs form (*Appendix E3: CRF\_3 Screening Labs*). Screening must occur no more than 30 days prior to implantation.

Screening will include the following:

1. Screening exam by investigator or co-investigator (*Appendix E2: CRF2\_PI Intake*). Includes Medical history, Current medications, Record contraceptive method for female subjects, Vital signs, Body Weight and Height, Physical exam, Evaluation of inclusion/exclusion criteria.
2. Sign Informed Consent Form (*Appendix A: Informed Consent*)
3. Dietician intake - Baseline body weight, height, ideal body weight, excess weight, BMI, (*Appendix E5: CRF5\_Dietician Intake*)
4. Laboratory tests\* plus EKG
5. Psychological evaluation (*Appendix E10: CRF10\_Consultation with Psychologist*)
6. Diabetic subject – follow up by provider or PI (*Appendix E11: CRF11\_Diabetic Patient Follow Up*)

\*Laboratory Tests (*Appendix E3: CRF3\_Screening Labs*) include:

CBC: Hgb, Hct, WBC, MCV, platelets

Chemistry panel: sodium, potassium, chloride, CO2, BUN, creatinine, glucose, SGOT/AST, SGPT/ALT, alkaline phosphatase, total bilirubin, total protein, albumin, total cholesterol, Fe/TIBC, B12, Folic Acid, 25-Hydroxy Vitamin D, TSH

Coag: Pro Time or INR, PTT

Urinalysis

HgbA1c (if diabetic)

H. Pylori Serology

Within 1 week of the screening tests, the PI will review the results and determine eligibility of the subject. The center will inform the subject of their results within 10 days of the tests. All potential subjects who pass the initial screening assessment must return for an additional visit within 7 days of the scheduled implantation procedure for the Pre-Implantation visit (*Appendix E4: CRF4\_Preimplantation Tests and Data*). This will include an assessment of the following:

- Urine pregnancy test (women of child-bearing potential)
- Medications List
- Weight (Note: This is the baseline weight that will be used for the endpoint assessments)

Subjects with a positive pregnancy test or who are taking medications listed in the exclusion criteria will be excluded from the study at this time, and will be considered to be screening failures.

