#### **4.3.2. Randomization**

Subject will be randomly assigned to treatment or control group with a 2:1 allocation as per a computer generated randomization schedule using variable block randomization using the following stratification factors: treatment center and then by BMI (<35 kg/m^2 vs. ≥ 35 kg/m^2). The randomization schedule will be created by the study statistician, and will remain confidential.

Subjects will not be informed of their randomization status until the day of implantation. Subjects randomized to the treatment group will proceed to implantation, and subjects randomized to the control group will proceed to an appointment with a dietician.

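### The primary ANCOVA for %TBL uses no continuous measure of baseline body size, so a little precision may be lost; the model is valid as written

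*Combined protocol and SAP*

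**What the plan says.** Section 7.1.2 specifies, for %TBL at 32 weeks, "an analysis of covariance that includes the effects of treatment group, study center, baseline BMI group", with the cut at 35 kg/m², and the subject's "gender as covariates". No continuous baseline covariate is listed.

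The same paragraph puts into the imputation model "Baseline body weight, baseline BMI, subject's gender, study center, treatment group, and all non-missing body weight measurements through Week 32". There, baseline BMI is named without grouping.

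Section 4.3.1 shows that both measures exist before treatment starts. The dietician intake records "Baseline body weight, height, ideal body weight, excess weight, BMI". Of the weight taken at the pre-implantation visit it says: "This is the baseline weight that will be used for the endpoint assessments".

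Section 4.3.2 stratifies randomization by "treatment center and then by BMI", with the same cut at 35. The endpoint in section 3.2.1 is "Percent change in total body weight (%TBL) at 32 weeks", so the outcome is already scaled by baseline weight.

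Section 7.2 sizes the trial with an SD of 6.6% and claims no reduction from covariates. Nothing in the document explains why continuous BMI or weight is left out of the ANCOVA.

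**The concern.** Eligible BMI runs from 30 to below 40. A single cut at 35 treats 30.1 and 34.9 as the same, and 34.9 and 35.1 as different. Stratification balances the two BMI groups between arms but not BMI within a group. Any relation between BMI and %TBL inside a stratum therefore stays in the residual variance, and chance imbalance there is not adjusted.

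What is at stake is the width of one confidence interval. The first co-primary endpoint succeeds if the lower 97.5% bound on the treatment difference exceeds 4.5 percentage points. The planning assumptions leave 2.54 points above that margin, at about 80% power. Precision from a variable already in the database would be worth having if it costs almost nothing.

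**Working it through.** **Inputs from section 7.2.** Control mean 3.3%, Spatz3 mean 10.34%, margin 4.5%, SD 6.6%, one-sided 2.5%, 160 and 80 evaluable subjects.

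**Reproducing the plan.**
- Distance above the margin: 10.34 − 3.3 − 4.5 = 2.54.
- SE = 6.6 × √(1/160 + 1/80) = 0.904.
- Power = Φ(2.54/0.904 − 1.96) = 80.2% (79.9% with the noncentral t).
- The formula gives 80 controls, hence 240 in all, as stated. No covariate gain is used.

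**Assumptions the documents do not supply.**
- r: the within-arm correlation of baseline BMI with %TBL, taken as linear and equal in both arms.
- k: the share of the linear BMI signal that the cut at 35 keeps, that is, the squared correlation of BMI with the two-level group. If BMI is uniform on 30 to 40, the group means are 5 apart and the variance is 100/12 = 8.33, so k = 5² × 0.25 / 8.33 = 0.75. Simulated truncated-normal shapes (means 33 to 36, SDs 2.5 to 3) give 0.65 to 0.68. An untruncated normal cut at its median gives 2/π = 0.64. The range used is 0.60 to 0.75.

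**Formulas.** Residual SD with the BMI group = 6.6 × √(1 − k r²). Residual SD with continuous BMI = 6.6 × √(1 − r²). Power follows as above. If the relation is linear, keeping the BMI group beside the continuous value leaves the second SD unchanged and uses one more degree of freedom.

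Where a range is shown, it runs from k = 0.75 to k = 0.60.

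| r | Power, BMI group | Power, continuous BMI | Gain (points) | Fall in residual variance |
|---|---|---|---|---|
| 0 | 80.2% | 80.2% | 0 | 0 |
| 0.1 | 80.5% | 80.6% | 0.1 to 0.2 | 0.3 to 0.4% |
| 0.2 | 81.4 to 81.2% | 81.8% | 0.4 to 0.6 | 1.0 to 1.6% |
| 0.3 | 82.9 to 82.4% | 83.8% | 0.9 to 1.4 | 2.4 to 3.8% |

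At r = 0.3 the half-width of the bound goes from 1.71–1.72 to 1.69 percentage points. The variance saving there equals about 6 to 9 evaluable subjects (240 × 0.024 to 240 × 0.038).

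**Is a larger r plausible?** With BMI uniform on 30 to 40 the SD is √8.33 = 2.89. The slope is r × 6.6/2.89 per BMI unit, which over 10 units is about 7 %TBL points at r = 0.3 and about 9 at r = 0.4. The whole assumed treatment difference is 10.34 − 3.3 = 7.04. A value of 0.3 is therefore already generous.

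**Cost of the extra term.** One degree of freedom costs about 1/240 = 0.4% of variance. This roughly cancels the gain at r = 0.1 and leaves a negligible loss at r = 0.

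**Sensitivity.** If 6.6% is instead the SD after adjustment for BMI group, power at r = 0.3 rises from 80.2% to 81.2–81.7%, a gain of 1.0 to 1.5 points. If baseline weight and BMI together explained a further 1%, 2% or 5% of residual variance, power would be 80.6%, 81.0% or 82.2%.

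**The case against.** The strongest reply is that the plan contains no error. Both stratification factors are in the model as randomized, which is standard and valid. The sample size relies on no covariate gain. The outcome is a percentage of baseline weight, so a remaining correlation with body size cannot be presumed. For baseline weight, gender probably carries part of the signal already. All of this stands, and it is why the point is an optional improvement and not a fault.

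A reader might go further and infer any of the following. The documents support none of them.

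- **That precision is certainly being thrown away.** This needs a correlation that the documents do not give, and at r = 0 there is no gain.
- **That BMI group is the only adjustment.** Center and gender are in the same model; what is missing is a continuous measure of body size.
- **That the richer imputation model is an inconsistency.** An imputation model that holds the analysis variables plus further predictors is good practice.
- **That the gain exceeds two power points.** This needs r of about 0.4 or more, which implies a BMI effect across the eligible range larger than the assumed treatment effect.

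It can also be said that a change to a co-primary model is not a trivial edit. Section 13 records statistical changes in versions 1.4 and 1.4a, the latter after FDA feedback, and section 10.2 sends amendments to FDA and the IRBs as appropriate. That is a fair account of the administrative cost. It does not remove the case for making the change if the section is opened before outcome data are seen.

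**Conclusion.** The point holds as a minor, optional gain in efficiency. The ANCOVA omits continuous baseline BMI and weight, which the trial already collects and uses for imputation, and some precision may be lost as a result. Replacing the two-level signal by continuous BMI is worth about 0 to 1.4 power points for r between 0 and 0.3, before the cost of the degree of freedom.

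This rests on a linear BMI effect, equal SDs in the arms, 6.6% as the SD before BMI adjustment, and a split that keeps 60% to 75% of the linear signal. The documents confirm none of these.

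No bias, type I error problem or sample-size error follows. The second co-primary endpoint is a single-arm proportion tested against 50% without covariates, so it gains nothing.

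**What to change.** In section 7.1.2, before outcome data are seen, add one continuous baseline covariate to the ANCOVA for %TBL: baseline BMI, or baseline weight. Keep study center, the BMI stratum and gender. State that the value is based on the pre-implantation weight, which section 4.3.1 already names as the endpoint baseline. The imputation model needs no change. The subgroup models in section 7.1.4 are built on the primary model and would inherit the covariate.

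The cost is one degree of freedom and a wording change to the protocol's statistics section, with whatever amendment step section 10.2 requires. No new data, visit or subject is needed.
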